1 INTRODUCTION

Pulmonary rehabilitation (PR) is “a comprehensive intervention based on a thorough patient assessment followed by patient-tailored therapies that include, but are not limited to, exercise training, education, and behaviour change, designed to improve the physical and psychological condition of people with chronic respiratory disease and to promote the long-term adherence to health enhancing behaviours”.(1) PR is highly effective in patients with chronic lung disease including chronic obstructive pulmonary disease (COPD), with large effects on health-related quality of life (QoL) and exercise capacity.(2) Its core components include exercise training, which is structured, progressive, and individually tailored, self-management education, outcome measurement, and it should be delivered by a multidisciplinary team of healthcare professionals. (3, 4) PR may relieve symptoms like dyspnoea and fatigue, improves emotional function and enhances the sense of autonomy.(5) Furthermore, evidence from Finland suggest that PR may reduce hospitalization days.(6) However, uptake of PR is limited. In a cross-sectional study of COPD patients in Canada, less than 1% of COPD patients had reportedly attended PR.(7) In the United States of America, 3.7 % of COPD patients attended PR in 2012.(8) Similarly, availability and accessibility of PR is probably limited in Finland, although we have no existing data from literature.

Currently available evidence suggests that telerehabilitation can be a safe alternative that is non-inferior to traditional centre-based pulmonary rehabilitation.(9) However, the existing evidence on digital interventions is still limited, especially regarding long term effects.(10)

As of Southwest Finland, rehabilitation programs for COPD patients have been on hold since the beginning of the COVID-19 pandemic – in first instance to prevent COVID-19 transmission in vulnerable patients, and in second instance because of lack of resources and/or prioritizing. In 2022-2023, the researchers of this study developed a remote rehabilitation program for COPD patients in a multidisciplinary team including a physiotherapist, a nutritional therapist, a smoking cessation nurse, in close collaboration with the commercial partner HealthFOX Oy. The program is to be incorporated in routine clinical care for COPD patients from April 2024.

2 STUDY OBJECTIVES AND PURPOSE

The general objectives of this pilot study are:

- To facilitate a safe rollout of the remote rehabilitation program for COPD patients in Southwest Finland.
- To identify and subsequently improve limitations of the rehabilitation program.
- To evaluate the levels of participant engagement and adherence to the digital COPD rehabilitation program over an extended period to understand its sustainability and long-term impact.
- To determine the effectiveness of the digital COPD rehabilitation program in improving lung function, exercise capacity, and quality of life among participants
- To assess the impact of the digital program on healthcare resource utilization, including hospital readmissions, emergency room visits, and outpatient visits related to COPD management.
- To measure participant satisfaction, usability, and overall experience with the digital platform to identify areas for improvement and enhance user engagement.
- To evaluate the cost-effectiveness of implementing the digital program compared to conventional rehabilitation methods, considering direct healthcare costs.

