3.2 General study outline and study schedule

Study subjects will be recruited from the 15th of April 2024 to the 30th of June 2026.

The rehabilitation program will be initiated preferably within one week but, at the latest within, 4 weeks from signing an informed consent, and the program will last up to 12 weeks. Follow-up will include 1 distant evaluation (questionnaires) at week 16 and a final visit at 26 weeks (+/- 2 weeks), including a 6-minute walking test. Follow-up may last up to 28 weeks from recruitment.

The final study report will be written in the years 2026-2027.

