5 CONTENT OF THE REHABILITATION PROGRAM

Development of the application

The application is not a clinical device but a communication tool between healthcare providers and patients. The rehabilitation program is developed by a team of TYKS healthcare workers of multiple disciplines in tight collaboration with HealthFOX. The multidisciplinary team included three pulmonologists (MK, MF, HS), one physiotherapist, two nutritional therapists, and one nurse specialized in smoking cessation.

Content of the rehabilitation program

Patients receive patient education materials throughout the program in text and video formats. These materials provide information on COPD management, lifestyle modifications, and strategies to enhance their well-being. Furthermore, the program contains an individually tailored exercise program., consisting of the following phases:

i. **Phase 1: Patient Assessment and Questionnaires**

- a. Patients are enrolled in the digital COPD therapeutics program through a referral from their healthcare provider or self-enrolment.
- b. Patients are prompted to complete a series of validated questionnaires and assessments, including:
 - i. CAT (COPD Assessment Test) questionnaire to assess their symptom severity.
 - ii. St George respiratory questionnaire, Finnish version
 - iii. Nutrition risk screening questionnaire (NRS2002) to evaluate their dietary habits and nutritional status.
 - iv. Physical activity participation questionnaire (unvalidated questionnaire that is currently used in TYKS clinical setting to score their current level of physical activity).
 - v. Smoking (Standardised nicotine dependence questionnaire, and stop smoking questionnaire) and alcohol question to assess their tobacco and alcohol consumption.
 - vi. Depression scale (DEPS) to screen for depression

ii. **Phase 2: Clinical Input and Evaluation**

- a. Review of clinical parameters by a medical doctor, including:
 - i. Pulmonary function test results (including spirometry)
 - ii. 6-minutes walking test

- iii. Blood test results, including hemoglobin, albumin, C-reactive protein, partial pressure of CO₂ (PCO₂).
- iv. Electrocardiogram
- v. Medication history
- vi. Current medications
- vii. And other relevant medical data.

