- b. The combination of patient input and clinical parameters is used to individualize the COPD therapeutics program for each patient. This will be done by the study investigators and healthcare professionals, and parts will be automatized. The automatically generated aspects will be evaluated and, if needed, adjusted by the study investigators and/or healthcare professionals.

- iii. **Phase 3: Individualized Program Development**
 - a. Patients who are identified as smokers are provided with a Cognitive Behavioural Therapy (CBT)-based program to support smoking cessation.
 - b. Based on the risk profile, participants are assigned to different types of breathing exercises, which are timed and progressively increased in intensity over time to improve lung function.
- iv. **Phase 4: Nutritional Advice**
 - a. Patients receive personalized nutritional advice based on **their input and nutritional status assessment**. The program aims to improve their dietary habits and overall nutritional status.
- v. **Phase 5: Physical Activity Program Initiation**
 - a. a physical activity program will start in the fifth week of the program. The intensity and duration of the program are determined based on their 6-minute walk test results according to the guidelines of the American College of Sports Medicine (ACSM) as applied in routine medical practice. Each patient receives an individually tailored program, which is approved by the TYKS physiotherapist. (11)
 - b. Over time, the program gradually increases the intensity and duration of the walking program to help patients build endurance.
- vi. **Phase 6: Strength Training**
 - a. After approximately eight weeks in the program, **depending on patients' clinical parameters** patients are introduced to strength training exercises to improve their overall physical strength and quality of life. Progression is slow and builds over time based on their risk profile.
- vii. **Phase 7: completing the program and follow-up**

- a. The training program finishes after 14 weeks. In this phase, the patient is interviewed about their experience
- b. In weeks 16 (+/- 2 weeks) and 26 (+/- 2 weeks), the symptoms will be scored with mMRC and St George respiratory questionnaire. In addition, a 6-minute walking test will be repeated in week 26 (+/- 2 weeks).

Tailoring of the program at the individual level

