6 OUTCOME VARIABLES

6.1 Assessment of efficacy

The single primary outcome measurement is distance in the 6 minutes walking test at 16 weeks in comparison to baseline to assess efficacy at the individual level. Secondary outcome includes 6 minutes walking test result at week 26 and St George Respiratory Questionnaire and 6 minutes walking test after 16 weeks and after 26 weeks in comparison to the result before initiation of the program. Other outcome measurements include the participant satisfaction, and other quantitative and qualitative measures of respiratory health and well-being.

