8 STATISTICS

8.1 Statistical hypotheses

8.2 Sample size

By recruiting 50 patients, we expect to recruit at least 12 patients from each of the following groups:

- According to exacerbations:
 - o Stable COPD patients
 - o COPD patients with acute exacerbations (AE-COPD)
- According to airflow limitation:
 - o GOLD 1-2 (Forced expiratory volume $\geq 50\%$ of predicted)

- GOLD 3-4 (Forced expiratory volume <50% of predicted)

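### Improvement in lung function is an effectiveness objective, but no lung-function measurement is scheduled after baseline; the cost-effectiveness comparison likewise has no comparator inside the study

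*Protocol*

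**What the plan says.** Section 2 lists seven general objectives. The fourth is "To determine the effectiveness of the digital COPD rehabilitation program in improving lung function, exercise capacity, and quality of life among participants". The seventh is to evaluate cost-effectiveness against conventional rehabilitation, counting direct healthcare costs.

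Section 5, Phase 2 lists, among the clinical parameters that a doctor reviews before the programme is individualised, "Pulmonary function test results (including spirometry". Phase 3 states that the breathing exercises are meant to improve lung function.

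Follow-up is described twice. Section 3.2: "Follow-up will include 1 distant evaluation (questionnaires) at week 16 and a final visit at 26 weeks", the latter with a walk test. Section 5, Phase 7: at weeks 16 and 26 "the symptoms will be scored with mMRC and St George respiratory questionnaire", and "a 6-minute walking test will be repeated in week 26".

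Section 6.1 sets the outcomes: "The single primary outcome measurement is distance in the 6 minutes walking test at 16 weeks in comparison to baseline". The secondary outcomes are further walk-test results and the St George questionnaire. The rest is general: "Other outcome measurements include the participant satisfaction, and other quantitative and qualitative measures of respiratory health and well-being".

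On costs, section 3.1 describes a single-arm observational pilot, section 4.1 says that no control group will be recruited, and section 1 says that local rehabilitation programmes have been on hold since the pandemic began. Section 10.1 lists patient records, the county COPD registry and the programme database as sources of study data.

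**The concern.** To determine whether a programme improves lung function, one needs at least a value before and a value after. The protocol provides for the first only. If a lung-function result is reported all the same, it will rest on whatever spirometry was done in routine care, at times that were not fixed and in patients whom the protocol did not choose. Patients tested again because of symptoms may differ from those who were not, and the mean change would then be biased by an amount that the study cannot estimate.

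The cost objective has a similar gap. The study can describe its own costs. A statement that the programme is more or less cost-effective than conventional rehabilitation needs costs and effects for the comparator, and none are collected in the study.

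**Working it through.** The protocol gives no figure to reproduce here. The check sets the objectives against the listed measurements and data sources.

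**Measurements as listed** (baseline from section 5, Phases 1 and 2; follow-up from section 3.2 and section 5, Phase 7):

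| Measure | Baseline | Week 16 | Week 26 | Named primary or secondary outcome in 6.1 |
|---|---|---|---|---|
| Lung function | yes | no | no | no |
| St George questionnaire | yes | yes | yes | yes |
| mMRC | no | yes | yes | no |
| 6-minute walk test | yes | no (but section 6.1 requires it) | yes | yes |

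**Lung function.** There are two follow-up points, weeks 16 and 26, and lung function is listed at 0 of 2. A change from baseline needs at least one later value, so none can be calculated from the scheduled measurements. Forced expiratory volume also appears in section 8.2, but there it defines groups that the investigators expect to recruit; it is not an outcome. The shortfall is 1 of the 3 components of the fourth objective, which is 1 of 7.

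**Quality of life.** The St George questionnaire is listed at all three points, so this component is covered.

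**Exercise capacity.** Section 6.1 makes the week-16 walk test the primary outcome. Section 3.2 describes week 16 as a remote questionnaire evaluation, and Phase 7 repeats the walk test at week 26 only. This is a separate contradiction that affects the primary outcome. It does not bear on lung function or costs, but it shows up in the same table.

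**Costs.** The objective names a comparator in general terms and a cost scope. Recruited comparator arms: 0 (sections 3.1 and 4.1). Local programmes that could serve as a concurrent comparator: none apparent, since they are on hold (section 1). Sources in section 10.1 that are tied to a comparator group: 0. A direct comparison within the study is therefore ruled out, and an indirect one is not described.

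**mMRC.** It is scored at weeks 16 and 26 with no listed baseline, so the listed measurements give no change from baseline.

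**The case against.** The strongest reply is that these are general objectives of a pilot. Section 6.1 fixes one primary outcome and names the secondary ones, and lung function is in neither group. Section 8.3 says that most data will be handled descriptively. No planned test fails for want of spirometry. This stands, and it limits the weight of the point.

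A second reply is that the wording is open. Section 3.2 says that the final visit includes a walk test, which does not exclude other tests. Section 6.1 allows other measures of respiratory health, and section 10.1 draws on patient records and a registry. In an observational study of routine care, using routine spirometry is ordinary. This stands in part: later values may well exist. Open wording still names no test, no time and no set of patients. An analysis plan could define how to use such values, but it cannot supply a measurement that was never scheduled.

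On costs, declining to recruit controls does not exclude historical or published ones. Local programmes existed before they were paused, and records or the registry might describe them. This also stands. A reader might infer that the cost comparison is impossible; the documents do not support that. They rule out only a direct comparison within the study.

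On mMRC, the Phase 1 list is open and the scale is not a named primary or secondary outcome. A baseline value is unlisted, not excluded.

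**Conclusion.** The point holds. As scheduled, the study cannot assess change in lung function, although an objective says that it will. The size is 1 of 3 components of 1 of 7 objectives, with lung function listed at 0 of 2 follow-up points. The comparative part of a second objective, cost-effectiveness, has no comparator within the study and no named external source.

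Two stronger readings are tempting. One is that a planned endpoint fails; it does not, because lung function is not a named primary or secondary outcome. The other is that no lung-function change could ever be reported, or that any reported change would be wrong by a known amount. Routine spirometry may exist, and the documents give neither a re-test rate nor any indication of how re-tested patients would differ, so the size of any bias cannot be stated.

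The conclusion assumes that the follow-up descriptions in section 3.2 and in section 5, Phase 7 list what is actually to be measured. If spirometry is in fact planned at a follow-up point, the defect is that the protocol does not say so. The missing mMRC baseline is minor. The week-16 walk-test contradiction matters more for the study as a whole, but it is a separate matter.

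**What to change.** 1. **Lung function.** Either remove it from the effectiveness objective and keep it as baseline description, or keep it and name a post-baseline measure taken from routine records within a fixed time window, labelled descriptive, with the number of patients re-tested reported. Neither option adds a visit or procedure. With the first, the stated aim of the breathing exercises goes untested in this study. With the second, the result remains open to selection in who is re-tested.
2. **Costs.** Restate the objective as a description of direct healthcare cost per participant. If the comparison is kept, call it indirect and fix the historical or published source of comparator costs and effects before the study's own costs are analysed. Restating is wording only and gives up the comparative claim; keeping the comparison also requires finding a suitable source.
3. **mMRC.** Add it to the Phase 1 questionnaires. This costs one short questionnaire per patient. For patients already past baseline, the value cannot be recovered.
4. **Walk test.** Reconcile section 6.1 with section 3.2 and section 5, Phase 7 on the week or weeks at which it is done.

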3 STUDY DESIGN

3.1 Type and design of the study

This is a single-arm observational pilot study.

3.2 General study outline and study schedule

Study subjects will be recruited from the 15th of April 2024 to the 30th of June 2026.

The rehabilitation program will be initiated preferably within one week but, at the latest within, 4 weeks from signing an informed consent, and the program will last up to 12 weeks. Follow-up will include 1 distant evaluation (questionnaires) at week 16 and a final visit at 26 weeks (+/- 2 weeks), including a 6-minute walking test. Follow-up may last up to 28 weeks from recruitment.

The final study report will be written in the years 2026-2027.

4 SUBJECT SELECTION

4.1 Source population

The source population comprises patients enrolled in the remote rehabilitation program for COPD patients in Southwest Finland. Patients will be selected from the inpatient- and outpatient clinics of Tyks Department of Lung Diseases and Allergology for enrolment in the rehabilitation program.

Whether or not one participates in the pilot study will not influence one's ability to join the program. No control group will be recruited for this study.

Whether or not one participates in the pilot study will not influence one's ability to join the program. No control group will be recruited for this study.

Healthcare professionals working with this study population and guiding them using the mobile application will also be included in the study for interview and feedback on their experience with working with digital tools to interact with patients and guide them through the rehabilitation plan. This will be voluntary and will not affect in any way their position in the workplace.

4.2 Number of subjects

Patients:

A maximum of 50 patients will be recruited for the pilot study.

Healthcare professionals:

All professionals involved in this study will be invited to participate in the feedback interviews.

4.3 Inclusion and exclusion

The study's inclusion criteria and rehabilitation program eligibility criteria can be found in Table 1.

For enrolment in the program, the clinician may deviate from the eligibility criteria on an individual basis, if agreed upon with the patient and the program coordinators and if safety issues are sufficiently addressed.

Table 1

Inclusion criteria for the pilot study	

 - Age 18 years or older - Participation in the remote rehabilitation program for COPD patients - Signed informed consent 	
Eligibility criteria for the rehabilitation program	Exclusion criteria for the rehabilitation program

 - Documented COPD diagnosis (ICD 10 code J44) - Expected survival > 1 year - Sufficient technical and language skills for safe participation in the program 	
 - Severe comorbidities with expected survival of less than 1 year, such as: 
 o active cancer o unstable heart disease o Substance dependence interfering with cognitive function o Clinically significant dementia 
Clinical suspicion that remote rehabilitation may be unsafe.

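### Documented COPD is a criterion of the programme but not of the study, so a programme waiver on diagnosis carries over into a study about COPD

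*Protocol*

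**What the plan says.** Table 1 in Protocol section 4.3 keeps two sets of criteria apart.

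- **Study inclusion:** "Age 18 years or older"; "Participation in the remote rehabilitation program for COPD patients"; "Signed informed consent". No separate study exclusions are listed.
- **Programme eligibility:** "Documented COPD diagnosis (ICD 10 code J44"), "Expected survival > 1 year", and enough technical and language skill to take part safely. A further column gives the programme's exclusions. These include severe comorbidity with survival expected to be under one year, and a clinical suspicion that remote rehabilitation may be unsafe.

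Above the table, section 4.3 says that for programme enrolment "the clinician may deviate from the eligibility criteria on an individual basis, if agreed upon with the patient and the program coordinators". It adds the condition that safety issues are sufficiently addressed. It does not say that any eligibility criterion is outside this discretion.

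Section 4.1 takes the programme's enrolled patients as the source population and adds that "Whether or not one participates in the pilot study will not influence" a patient's ability to join the programme. Section 2 states the objectives in terms of a COPD rehabilitation programme and its rollout to COPD patients. Section 8.2 expects 12 or more patients in each of four groups: stable COPD and COPD with acute exacerbation, and GOLD 1-2 and GOLD 3-4.

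**The concern.** Discretion over who receives a routine-care programme is a clinical matter and is not questioned here. The difficulty is that the same discretion also settles who is in the research population. Because programme participation is itself a study criterion, and diagnosis is not, a decision made for care passes straight into the study.

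The primary outcome is the change in six-minute walk distance from baseline to week 16, and the St George questionnaire is secondary. In a single-arm study these changes are interpreted by reference to the population they come from. If some participants do not have COPD, the result no longer describes only the population named in the objectives, and those participants have no proper place in the section 8.2 groups, all of which presuppose COPD.

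**Working it through.** This is mainly a matter of reading the criteria together. The protocol states no effect size, standard deviation or power, so there is no sample-size figure to reproduce.

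**Route into the study**

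1. Study entry requires age, programme participation and consent (section 4.3, Table 1).
2. Programme participation normally requires J44 (same table), so COPD is required indirectly, by default.
3. The clinician may set aside a programme eligibility criterion for an individual, with the patient's and the coordinators' agreement and with safety addressed (section 4.3). J44 is one of those criteria and is not exempt.
4. A patient enrolled by waiver of J44 is a programme participant, and so meets step 1 with age and consent. The conditions in step 3 concern agreement and safety; neither brings the diagnosis back.
5. Section 6.1 defines the efficacy outcomes without limiting them to patients who met the programme criteria.

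**Size per patient**

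Input: at most 50 patients (section 4.2). The number waived on diagnosis, w, is not given and is an assumption below. Share of the sample = w/50:

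| w (assumed) | share of 50 |
|---|---|
| 1 | 2% |
| 3 | 6% |
| 5 | 10% |
| 10 | 20% |

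If waived patients change on average by d metres more or less than the others, the overall mean change moves by (w/50) × d: 0.02d for one patient and 0.10d for five. The protocol gives no basis for d.

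**Effect on the section 8.2 groups**

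As an illustration, let n = 50 − w be the patients with COPD and p the share in the smaller half of one split (assumed). The chance that both halves reach 12 is the binomial probability P(12 ≤ X ≤ n − 12), with X ~ Bin(n, p):

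| n | p = 0.24 | p = 0.30 | p = 0.40 | p = 0.50 |
|---|---|---|---|---|
| 50 | 0.55 | 0.86 | 0.99 | 1.00 |
| 47 | 0.46 | 0.79 | 0.99 | 1.00 |
| 45 | 0.39 | 0.74 | 0.98 | 1.00 |
| 40 | 0.24 | 0.56 | 0.93 | 0.99 |

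With few waivers and balanced groups the loss is negligible. It shows only if one group holds roughly 24-30% of patients.

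**The case against.** The strongest reply is that the programme is for COPD, that J44 heads its criteria, and that patients come from a lung department. A patient without COPD enters only if clinician, patient and coordinators all agree, and nothing suggests that this is planned. Moreover, an observational pilot of routine care may reasonably study whoever actually receives the programme, especially when safe rollout is its first objective. An analysis plan that is not shown may also define the efficacy set. Most of this stands, and it limits the size of the point. It does not close the route, because study eligibility is fixed in the protocol and Table 1 leaves diagnosis to a criterion that can be waived.

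Four stronger readings are tempting but are not supported:

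- **Patients with a poor prognosis enter freely.** The waiver names the eligibility criteria. The separate exclusion column, which nothing says can be waived, still bars severe comorbidity with survival expected under one year. Many such patients remain excluded. Nor does a prognosis under one year imply death within a follow-up of up to 28 weeks.
- **The report could not tell non-COPD patients apart.** Patient records and the COPD registry are source data (section 10.1), spirometry is reviewed at entry (section 5), and the eCRF covers comorbidities and COPD characteristics (section 10.4). They could be identified. What section 10.4 does not name is a record of which criterion was waived, although its list is not presented as complete.
- **Patients without obstruction would be graded GOLD 1-2.** Section 8.2 heads that split "According to airflow limitation". The volume cut-off in brackets separates the two groups; it does not say that patients without airflow limitation are graded.
- **A large part of a subgroup could be affected.** That requires assuming both several waivers and that they fall in one group at its minimum of 12. The protocol supports neither.

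**Conclusion.** The point holds in a limited form. As written, a patient admitted to the programme by waiver of the diagnosis criterion is also eligible for the study, while the study's objectives and subgroups concern COPD. This follows from section 4.3 alone and needs no numerical assumption.

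Its size is unknown. Each such patient is 2% of a full sample of 50, and more if fewer are recruited. With no waiver rate stated, the total may be small or zero. No bias in walk distance can be estimated from the protocol. The case for acting rests on the low cost of closing the gap, not on a demonstrated distortion of the result.

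**What to change.** - In Table 1, add a documented COPD diagnosis (J44) to the study inclusion criteria, so that a programme waiver on diagnosis does not carry over into the study.
- Add one eCRF field recording any other programme criterion waived for a participant, such as survival or technical and language skills.
- Keep participants with such a waiver in the safety and engagement reports, and give the primary walk-distance change and the St George change with and without them. Patients waived on diagnosis would not be in the study, so this comparison concerns the other criteria only.

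The cost is amendment wording, one data field and one additional presentation of two outcomes. The downside is that a few programme patients may not enter the study. Their access to the programme is unchanged under section 4.1, and the programme's own admission rule is left to the clinicians.
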